7. STUDY POPULATION

7.1. Enrollment by Investigator

Enrollment by geographic region (North America, Europe, Asia/Pacific, and Other), country, and investigator will be summarized.

7.2. Subject Disposition

For the open-label treatment period, the subject disposition summary will be based on the enrolled analysis set and will include counts and percentages of subjects who:

- Enrolled
- Enrolled and were treated with study treatment
- Completed the open-label treatment period
- Did not complete the open-label treatment period, overall and by the reason for not completing it: adverse event, lost to follow-up, physician decision, pregnancy, protocol violation, study terminated by sponsor, withdrawal by subject, failure to meet open-label continuation requirement at Visit 3 (Day 29), or other
- Continued to the randomized withdrawal treatment period
- Did not continue to the randomized withdrawal treatment period

For the randomized withdrawal treatment period, the subject disposition summary will be based on the randomized analysis set and will include counts and percentages of subjects who:

- Were randomized
- Were randomized and treated with study treatment
- Completed the randomized withdrawal treatment period
- Did not complete the randomized withdrawal treatment period, overall and by the reason for not completing it: adverse event, lost to follow-up, physician decision, pregnancy, protocol violation, study terminated by sponsor, withdrawal by subject, or other
- Completed the study
- Did not complete the study
- Continued to Study 0171
- Did not continue to Study 0171

Listings of subject disposition (one for the open-label treatment period and one for the randomized withdrawal treatment period) will include the date the informed consent form was signed, dates of first dose and last dose of study drug, primary reason for discontinuation of study treatment, study completion status, and primary reason for study termination.

7.3. Protocol Deviations

Summaries of major protocol deviations will include counts and percentages of subjects who have any major protocol deviations and counts and percentages of subjects who have major protocol deviations in each category. A by-subject listing of all protocol deviations will be provided.

7.4. Medical History and Medical Conditions Present at Entry

Medical history will be mapped according to [REDACTED] and summarized by system organ class and preferred term.

7.5. Demographic and Baseline Characteristics

Summaries of demographic and baseline characteristics will include the following: age (years), age category (< 65 years, ≥ 65 years), sex, race, ethnicity, weight (kg), height (cm), BMI (kg/m²), smoking status (Never, Current, Former, Missing), Diagnosis of Primary Autonomic Failure (Multiple System Atrophy, Parkinson's Disease, Pure Autonomic Failure), OHSA#1 score, OHSA Composite Score, OHDAS Composite Score, OHQ Composite Score, 10 min Supine SBP (mmHg), 10 min Seated SBP (mmHg), 3 min Standing SBP (mmHg), and NE (pg/mL).

For the open-label treatment period, this summary will be presented for the open-label safety analysis set. For the randomized withdrawal treatment period, this summary will be presented for the randomized withdrawal FAS.

8. EFFICACY

8.1. General Considerations

The efficacy data collected in the open-label treatment period will be summarized descriptively. Nominal p-values will be provided as appropriate for randomized withdrawal treatment period efficacy data analyses.

8.2. Statement of the Null and Alternate Hypotheses for the Primary Endpoint

The primary efficacy endpoint is the proportion of treatment failure at Week 6, the end of the randomized withdrawal treatment period.

The null hypothesis is that there is no difference between the proportion of treatment failure in subjects receiving TD-9855 (P_{Active}) and the proportion of treatment failure in subjects receiving placebo ($P_{placebo}$) at Week 6 during the randomized withdrawal treatment period. The alternative hypothesis is that they differ:

$$H_0 : P_{Active} = P_{placebo}$$
$$H_1 : P_{Active} \neq P_{placebo}$$

8.3. Subgroup Analyses

Subgroup analyses will characterize the consistency of the treatment effect across the specified subgroups (Section 6.2.8).

8.4. Analysis of the Primary Efficacy Endpoint

8.4.1. Primary Efficacy Analysis

A logistic regression model will be fitted to estimate the effect of treatment on the primary endpoint. The model will include terms for treatment and baseline disease type (MSA, PAF, PD) and will include baseline OHSA#1 score and baseline PGI-S as continuous covariates. (Including baseline OHSA#1 and baseline PGI-S as continuous covariates models the effect of a 1-point increase in baseline score as multiplying the odds of failure by the same constant, regardless of the score.) Point estimates and 95% CIs for odds ratios will be presented. Also presented will be “least squares” treatment failure proportions (point estimates and standard errors) for each treatment and disease type.

In addition, the proportions of subjects with at least a 1-point worsening in OHSA#1 and at least a 1-point worsening in PGI-S will be summarized separately by postbaseline visit, and stratified (by baseline score) Cochran-Mantel-Haenszel test p-values for testing equality of TD-9855 and placebo worsening rates and mean scores at each postbaseline visit will be included. A 2×2 table showing concordance (OHSA#1 worsening status (Yes/No) by PGI-S worsening status (Yes/No)) at Week 6, with Cohen’s kappa measure of agreement statistics, will also be provided.

A listing by treatment group for all FAS subjects will be provided, to include subject ID, baseline disease type (MSA, PAF, PD), baseline OHSA#1 score, baseline PGI-S score, change from baseline OHSA#1 score at Week 22, change from baseline PGI-S score at Week 22, and treatment failure status (Yes/No).

Additional Analyses of the Primary Efficacy Endpoint

PP Analysis

The primary efficacy analysis will be repeated for the PP analysis set.

Missing Data Handling

For the primary efficacy analysis, subjects who did not complete the Week 6 visit because the study was terminated early by the sponsor are counted as treatment failures, like all other subjects who failed to complete the randomized withdrawal period. The primary efficacy analysis will be repeated excluding these subjects.

Subgroup Analyses

To assess consistency of treatment failure TD-9855:placebo odds ratios across subgroups, the analysis of the primary endpoint will be repeated for each of the subgroups specified in Section 6.2.8.

A forest plot will be provided showing the TD-9855:placebo odds ratio point estimates and 95% CIs for each subgroup.

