5.1. Description of Study Medications

For OL treatment period:

All subjects will receive TD-9855 once daily through the end of the treatment period.

For randomized treatment period:

Subjects will be randomized in a 1:1 ratio to receive either TD-9855 (test product) or PBO (reference product) once daily through the end of the treatment period.

Further details regarding study medication handling, storage, and destruction are found in a separate pharmacy manual.

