8.2. Sample Size and Power

Assuming that 60% are eligible for randomization at the end of the 16-week OL period, approximately 258 subjects will be enrolled such that 154 subjects are expected to continue into the randomized treatment period. For the De Novo Group, the goal is to enroll at least 40% of MSA subjects.

The primary analysis will occur when all subjects in the Full analysis set (FAS) (Section 8.3.2) of double-blinded randomized withdrawal phase of the study have either completed the primary endpoint assessment (OHSA#1 and PGI-S at Week 6 post randomization) (V9, D155) or discontinued earlier and the database has been cleaned and locked. A sample size of 154 at randomization will provide an overall power of 90% to detect a difference of 25% (25% TD-9855 vs. 50% PBO) in the primary endpoint of proportion of subjects that meet the criteria of treatment failure at Week 6 (V9, D155) during the double-blind randomized withdrawal phase at two-sided alpha level of 0.05.

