8.5.1.1. Primary Efficacy Evaluation

The primary study endpoint is the proportion of treatment failure at Week 6 during the double-blind randomized withdrawal phase. Treatment failure is defined as subjects who meet the following criteria at Week 6 following randomization:

Change (worsening) from baseline in OHSA#1 score of 1.0 point and worsening of disease severity as assessed by a 1-point change in PGI-S.

The assessments done at the Week 16 (V6, D113) visit in the OL phase prior to randomization are considered baseline for the double-blind randomized withdrawal phase of the study. Subjects who withdraw for any reason prior to V9 (D155) or subjects who fail to provide assessment at V9 (D155) will be considered as treatment failures.

Logistic regression model will be used to compare treatment differences based on the FAS. The model will include fixed effect class terms of treatment, baseline disease type (MSA, PAF, PD), and continuous covariate of baseline OHSA#1 score, and baseline PGI-S score. Odds Ratio with 95% confidence intervals will be calculated and presented, least-square proportion and 95% confidence intervals on the differences between TD-9855 and placebo groups will be calculated and presented. In addition, the proportion of subject with treatment failure along with proportion of subjects failing separately due to worsening of OHSA#1 and PGI-S will be reported.

Sensitivity analyses on the primary endpoint will be carried out (1) using per-protocol set which excludes subjects with major protocol deviations, (2) using multiple imputation for subject missing OHSA#1 and/or PGI-S score at Week 6 post randomization (V9, D155) and (3) by excluding subjects with missing data on primary endpoint. Additional sensitivity analyses may be defined in the SAP.

The primary analysis will be repeated on a set of pre-specified subgroups (e.g., disease type) and presented in graphical format. Details will be specified in the Statistical Analysis Plan (SAP).

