11.2. Changes to Protocol-Specified Analyses

- Removal of smoking status subgroups
- Addition of baseline norepinephrine subgroups
- To the planned analyses of standing SBP at 3 minutes and at 10 minutes during the orthostatic standing test, addition of similar analyses of standing heart rate at 3 minutes and at 10 minutes

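### SAP 8.4.1 omits the protocol's 95% CI on the between-arm difference in failure proportions, the scale on which the trial is sized, and SAP 11.2 does not record the change

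*SAP*

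**What the plan says.** **Protocol 8.5.1.1** (same content in the synopsis) plans three things for the primary endpoint besides the test: the odds ratio with a 95% CI; "least-square proportion and 95% confidence intervals on the differences between TD-9855 and placebo groups will be calculated and presented"; and the proportion of subjects who fail, with the two components shown separately.

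**Protocol 8.2** gives an "overall power of 90% to detect a difference of 25% (25% TD-9855 vs. 50% PBO) in the primary endpoint". **SAP 8.2** states the null hypothesis as equality of the two failure proportions.

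**SAP 8.4.1** keeps the logistic model and the odds ratios with 95% CIs. On the proportion scale it adds least-squares "treatment failure proportions (point estimates and standard errors) for each treatment and disease type". It also plans component worsening proportions by visit with Cochran-Mantel-Haenszel p-values, a concordance table with kappa, and a subject listing by treatment group that includes failure status. The forest plot, and the gate to the secondary endpoints in SAP 8.6, use the odds ratio.

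**SAP 8.5** gives every secondary endpoint a between-arm difference with standard error, 95% CI and p-value.

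**Protocol 8.1** requires changes to the planned analyses to be described in the SAP. **SAP 11.2** lists three, the first being "Removal of smoking status subgroups"; the others are the norepinephrine subgroups and standing heart rate. None concerns the primary effect measure.

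**The concern.** The endpoint, the hypothesis and the sample size are all expressed as proportions, yet the SAP plans no interval on that scale. With failures as common as the design assumes, an odds ratio cannot be read as a difference, because the same odds ratio corresponds to different differences at different placebo rates. Separate standard errors for two proportions from one fitted model do not supply the missing interval either. The estimates are correlated and no covariance is planned.

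The least-squares proportions are a second, conditional issue. Under a common convention they are predictions at the covariate means with the three disease types weighted equally. Such a prediction describes an artificial average patient, and its difference between arms need not be the difference in failure rates.

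At stake is the pre-specified estimate of how large the benefit is. The test of whether there is one is not in question.

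**Working it through.** **1. Inputs from the protocol.** Failure 25% vs 50%, 154 randomized, 90% power, two-sided alpha 0.05 (8.2); 1:1 allocation (5.1), so 77 per arm. The SAP's sample-size section is redacted, so the sizing scale comes from the protocol.

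**2. Reproduce the plan's figure.** Pooled two-proportion formula, mean rate 0.375:

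n per arm = [1.960·√(2·0.375·0.625) + 1.282·√(0.25·0.75 + 0.50·0.50)]² / 0.25² = (1.342 + 0.848)² / 0.0625 = 76.7, rounded up to 77. Total 154, power 90.1%.

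A log-odds-ratio formula gives (1.960 + 1.282)²·(1/0.1875 + 1/0.25)/(ln 3)² = 10.51·9.333/1.207 = 81.3, rounded up to 82, total 164. The stated 154 matches the proportion scale.

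**3. The omitted interval at the design rates.** SE = √(0.1875/77 + 0.25/77) = 0.0754; half-width 1.96·0.0754 = 0.148. The difference is −25.0 points, 95% CI −39.8 to −10.2 (Newcombe −38.7 to −9.7). For the same data the unadjusted odds ratio is 0.33, 95% CI 0.17 to 0.66.

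**4. The odds ratio does not determine the difference.** Holding it at 1/3:

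| Placebo failure | TD-9855 failure | Difference (points) |
|---|---|---|
| 10% | 3.6% | −6.4 |
| 20% | 7.7% | −12.3 |
| 50% | 25.0% | −25.0 |
| 80% | 57.1% | −22.9 |
| 90% | 75.0% | −15.0 |

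**5. Least-squares proportions, if the usual convention is used.** None of these inputs is in the documents. Assumptions: MSA/PD/PAF mix 40/50/10, PAF shifted on the log-odds scale with MSA and PD equal, and the baseline scores acting together as a normal covariate with SD 0 or 1 on the logit scale. For each case, solve the intercept a and treatment effect b so that the average of expit(a + disease + covariate) is exactly 50% on placebo, and exactly 25% with b added. The least-squares proportion is then expit(a + mean of the three disease effects), with b added for TD-9855.

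| PAF log-odds shift | Covariate SD | LS placebo | LS TD-9855 | LS difference (points) | Conditional OR |
|---|---|---|---|---|---|
| 0 | 0 | 50.0% | 25.0% | 25.0 | 0.33 |
| −1.6 | 0 | 40.3% | 17.8% | 22.4 | 0.32 |
| +1.6 | 0 | 59.7% | 31.7% | 28.0 | 0.31 |
| 0 | 1 | 50.0% | 21.2% | 28.8 | 0.27 |
| −1.6 | 1 | 40.4% | 15.0% | 25.4 | 0.26 |
| +1.6 | 1 | 59.6% | 27.4% | 32.2 | 0.26 |

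(Differences are taken before rounding.) By hand for the second row: a = 0.14 gives 0.9·expit(0.14) + 0.1·expit(−1.46) = 0.50, and expit(0.14 − 1.6/3) = 0.403. With PAF at 15% the range over the same shifts is 23.4 to 32.2.

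The true difference is 25 points in every row. In the fifth row the difference is nearly right although both proportions are about 10 points too low. An odds ratio near 0.26 needs the covariate effect; disease effects alone leave it at 0.31 to 0.32.

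**The case against.** The strongest reply is that this is a one-line reconciliation between two documents. Silence in the SAP may be an oversight that leaves the protocol's output in force, and the primary test, type I error and gate do not change. That stands: the text does not show that the interval was dropped on purpose.

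A reader might infer that the arms' observed failure rates will go unreported. The documents do not support this. Protocol 8.5.1.1 promises the failure proportion, and the SAP listing carries each subject's failure status. What is missing is an explicit SAP table by arm and any difference with an interval; a listing is not a pre-specified estimate.

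A reader might also infer that the SAP's least-squares proportions are definitely not the arms' failure rates. The SAP states no weighting or back-transformation, and its sample code is in a separate file (SAP 11.3). The phrase about treatment and disease type could even mean treatment-by-disease cells, where equal disease weighting does not arise. Step 5 of the working is therefore conditional. The gap between conditional and unadjusted odds ratios there is ordinary non-collapsibility, not an error.

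Finally, the protocol's own difference is attached to least-squares proportions, so restoring its wording alone would leave the method undefined. That is correct. The standardized proportions proposed below are a change of method and should be declared as one.

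**Conclusion.** The point holds as an undeclared omission on the primary endpoint: the protocol commits to a 95% CI on the difference in failure proportions, SAP 8.4.1 does not plan it, and SAP 11.2 does not say so. This rests on the unredacted text alone. The missing interval is about ±15 points at the design rates with 77 per arm, and wider if fewer are randomized.

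The least-squares part is weaker. If the usual convention applies, the planned proportions need not match the arms' failure rates, and their difference is roughly 22 to 32 points against a true 25 under assumptions that the documents neither give nor exclude. If the covariates are not prognostic, there is no discrepancy. The consequence is confined to estimation and reporting, so this should be fixed but does not threaten the test.

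**What to change.** In SAP 8.4.1:

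- Keep the logistic odds ratio with its CI as the primary test.
- Report observed failures as n/N by arm, as the protocol promises.
- Add the covariate-standardized failure proportion per arm: from the fitted model, predict each FAS subject's failure probability under TD-9855 and again under placebo, and average each set over all FAS subjects.
- Report the difference of the two averages with a 95% CI, by the delta method or bootstrap, and name which.
- If the least-squares proportions stay, state their disease weights and covariate values, and do not use them for the treatment comparison.

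In SAP 11.2, record the change from the protocol's least-squares proportions to standardized ones, with the reason.

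The cost is a few lines of SAP wording and one computation from a model already being fitted. No new data are needed, and the test, alpha and testing sequence do not change.

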The Logistic regression model will be used to compare treatment differences based on the FAS. The model will include fixed effect class terms of treatment, baseline disease type (MSA, PAF, PD), and continuous covariate of baseline OHSA#1 score, and baseline PGI-S score. Odds ratio with 95% confidence intervals will be calculated and presented, least-square proportion and 95% confidence intervals on the differences between TD-9855 and PBO groups will be calculated and presented. In addition, the proportion of subject with treatment failure along with proportion of subjects failing separately due to worsening of OHSA#1 and PGI-S will be reported.

Sensitivity analyses on the primary endpoint will be carried out (1) using per-protocol set which excludes subjects with major protocol deviations, (2) using multiple imputation for subject missing OHSA#1 and/or PGI-S score at Week 6 post randomization (V9, D155) and (3) by excluding subjects with missing data on primary endpoint.

The primary analysis will be repeated on a set of pre-specified subgroups (e.g., disease type) and presented in graphical format. Details will be specified in the Statistical Analysis Plan (SAP).

Secondary efficacy endpoints involving assessment of change from baseline at multiple time points such as OHSA#1, OHSA composite score, OHDAS composite score, and percent of

PROTOCOL SYNOPSIS (CONTINUED)

time spent in supine, sitting, and standing position as measured by a wearable device, will be analyzed using mixed model for repeated measures (MMRM) to compare treatment differences based on the FAS. The model will include fixed effect class terms of treatment, baseline disease type (MSA, PD, PAF), week, and continuous covariate of baseline score of the respective scale, a random subject effect, with an unstructured covariance structure. If the model doesn't converge, compound symmetry or other covariance structures will be used as alternative covariance structure. Least-square means and 95% confidence intervals on the differences between TD-9855 and PBO will be calculated and presented.

Exploratory endpoints involving assessment of change from baseline at multiple time points such as standing SBP during orthostatic standing test will be analyzed similarly.

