8.7. Missing Data Handling

Missing data in the MMRM analysis is assumed as missing at random (MAR) and will not be imputed for the analysis of the primary endpoint. Sensitivity analyses on the primary endpoint will be conducted using multiple imputation and excluding subjects with missing data on primary endpoint.

Rules for imputation of missing safety data (e.g., missing or partial AE start dates) will be specified in the SAP. General principles are to count AEs as treatment emergent if they might have been, given the data obtained, and likewise to count medications as concomitant if they might have been, given the data obtained. There will be no imputation of missing safety assessments (e.g., laboratory test results).

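### SAP 8.4.1 drops the protocol's multiple imputation and difference in failure proportions, narrows its missing-excluded rerun, and SAP 11.2 records none of it

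*SAP*

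**What the plan says.** **Protocol.** Section 8.5.1.1, matched by the synopsis, lists three sensitivity analyses of the primary endpoint. One uses the per-protocol set. The second is specified as "using multiple imputation for subject missing OHSA#1 and/or PGI-S score at Week 6 post randomization (V9, D155". The third is done "by excluding subjects with missing data on primary endpoint". Section 8.7 repeats the last two: "Sensitivity analyses on the primary endpoint will be conducted using multiple imputation and excluding subjects with missing data on primary endpoint". For effect size, 8.5.1.1 asks for odds ratios with intervals and adds that "least-square proportion and 95% confidence intervals on the differences between TD-9855 and placebo groups will be calculated and presented". Section 8.1 says that changes to the planned analyses will be described in the SAP.

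**SAP.** Section 8.4.1 keeps the per-protocol rerun. Under its missing-data heading it deals only with subjects who missed Week 6 because the sponsor terminated the study, and says: "The primary efficacy analysis will be repeated excluding these subjects". For effect size it gives odds ratios with 95% intervals and least-squares "treatment failure proportions (point estimates and standard errors) for each treatment and disease type". It also plans "A 2×2 table showing concordance (OHSA#1 worsening status (Yes/No) by PGI-S worsening status (Yes/No)) at Week 6", and for the individual data "A listing by treatment group for all FAS subjects will be provided". Section 11.2 lists three changes from the protocol: smoking subgroups removed, baseline norepinephrine subgroups added, and standing heart rate analyses added.

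**The concern.** SAP 6.4.7 makes any withdrawal or missed Week 6 assessment a failure. That rule is part of the endpoint, so more dropout in one arm is a real difference on that endpoint and not in itself an artefact. It does mean that the result can rest partly on who left and partly on whose symptoms worsened. The two protocol reruns were there to show how far it rests on each.

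Under the SAP text that check covers sponsor terminations only. Subjects who leave for adverse events, by their own choice, or who miss the visit stay in as failures in every planned fit of the composite, apart from any whom the per-protocol criteria remove for other reasons.

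The trial was also sized on a difference in proportions (Protocol 8.2), and the SAP no longer plans to report that difference with an interval. A reader who relies on 11.2 would believe that the protocol's sensitivity analyses survive.

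**Working it through.** **1. Set the texts side by side.**

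| Item | Protocol 8.5.1.1 / 8.7 | SAP 8.4.1 | SAP 11.2 |
|---|---|---|---|
| Per-protocol rerun | required | kept | not needed |
| Multiple imputation of Week 6 OHSA#1 / PGI-S | required | absent | not listed |
| Rerun without any subject missing the endpoint | required | sponsor terminations only | not listed |
| Difference in failure proportions, 95% CI | required (8.5.1.1) | absent; proportions with SEs only | not listed |

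**2. Rule out other explanations.** SAP 8.4.1 and 11.2 show no blacked-out text. The SAP contents list shows that 11.1 on missing data covers only adverse event severity, event dates, medication dates and laboratory values. The per-protocol exclusions in 6.2.7 do not include a missing Week 6 visit. The logistic sample code (11.3) is in a separate file that was not supplied, so this point concerns the SAP text only.

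**3. Reproduce the sample size.** Inputs from Protocol 8.2: failure 25% on TD-9855 and 50% on placebo, two-sided alpha 0.05, power 90%, 154 randomized; 1:1 allocation from Protocol 5.1.

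n per arm = [1.96·√(2·0.375·0.625) + 1.2816·√(0.25·0.75 + 0.50·0.50)]² / 0.25² = 76.7, rounded up to 77, so 154 in total. Power at 77 per arm is 0.901. The plan's figure reproduces.

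At these rates the omitted estimate is 25.0 points (placebo minus active). Its SE is √(0.1875/77 + 0.25/77) = 0.0754, giving an unadjusted 95% CI of 10.2 to 39.8.

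**4. Illustrate how much the missing-as-failure rule can move the result.** The documents give no dropout rate after randomization, so the rates here are assumed. Let d be dropout, q the failure rate among completers, and p the failure rate with missing counted as failure:

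p = d + (1 − d)·q, so q = (p − d)/(1 − d)

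The primary analysis uses 77 per arm; complete-case uses 77·(1 − d). Intervals are Wald and unadjusted. The protocol does not say whether 25%/50% already counts missing as failure, so both readings are shown.

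- *Reading A: 25%/50% are p.* The primary difference is 25.0 (10.2 to 39.8) at any dropout.
- *Reading B: 25%/50% are q.* The complete-case difference is 25.0 at any dropout.

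| Dropout, active/placebo | A: complete-case difference (95% CI) | A: gap | B: primary difference (95% CI) | B: gap |
|---|---|---|---|---|
| 5%/5% | 26.3 (11.5 to 41.1) | 1.3 | 23.8 (8.7 to 38.8) | 1.25 |
| 10%/10% | 27.8 (13.2 to 42.4) | 2.8 | 22.5 (7.2 to 37.8) | 2.5 |
| 10%/20% | 20.8 (5.9 to 35.8) | 4.2 | 27.5 (12.4 to 42.6) | 2.5 |
| 20%/10% | 38.2 (25.0 to 51.4) | 13.2 | 15.0 (−0.6 to 30.6) | 10.0 |

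Worked example, A at 20%/10%: q active = (0.25 − 0.20)/0.80 = 6.25%; q placebo = (0.50 − 0.10)/0.90 = 44.4%; difference 38.2.

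Worked example, B at 20%/10%: p active = 0.20 + 0.80·0.25 = 40%; p placebo = 0.10 + 0.90·0.50 = 55%; difference 15.0.

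**The case against.** **The protocol still specifies the reruns.** The SAP nowhere withdraws them, so running them would not be wholly post hoc. That is fair. But the SAP sets out its own missing-data handling for this endpoint and leaves them out, and neither document gives an imputation model. Its key choices would still have to be made later.

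**Related output is planned.** SAP 6.4.5 and 6.4.6 summarize worsening of each component both ways, on recorded scores and with missing counted as worsened. Section 8.4.1 adds stratified Cochran-Mantel-Haenszel tests between arms at each visit. Section 8.5 fits repeated-measures models to both components assuming data missing at random, and 7.2 tabulates non-completion by reason. This narrows the gap, but none of it re-estimates the treatment effect on the composite. The listing holds the outcome and every model covariate, so a complete-case refit is possible, but it is not planned.

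**The difference is mostly presentation.** The point difference is a subtraction, and an approximate interval follows from the standard errors. The decision in SAP 8.6 rests on the odds ratio and its p-value. This lowers the weight of that item without removing the protocol's commitment.

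**The scenarios are invented.** They use 77 per arm, which may not apply: the SAP describes randomization in the past tense and provides for sponsor termination. The 13.2-point case needs a 6.25% failure rate among active completers. This stands, and the table shows sensitivity only.

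**Recording and protocol wording.** Protocol 8.1 asks for changes to be described in the SAP, not in 11.2 specifically. These are described nowhere in its visible text. Protocol 8.7 also has a confused sentence tying non-imputation in the repeated-measures model to the primary endpoint, but the next sentence states the imputation commitment plainly.

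**Conclusion.** The concern holds. Multiple imputation and the difference in failure proportions with its interval are absent from the SAP text. The exclusion rerun is narrowed from all missing primary endpoints to sponsor terminations. None of the three changes is recorded.

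The consequence is limited. Protocol 8.5.2 treats sensitivity analyses of the primary endpoint as descriptive, and type I error, the 154 subjects and the primary test are untouched. Under the assumed scenarios the lost check would show little when dropout is low and balanced, with a gap of 1.25 to 2.8 points at 5% to 10% per arm. It would show more when dropout is unbalanced: 2.5 to 4.2 points at 10%/20% and 10.0 to 13.2 at 20%/10%. In one of those cases the primary interval crosses zero while the complete-case difference stays at 25.0.

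No scenario is claimed to be likely. Complete-case is a comparison, not the truth. The point should be corrected, but it does not threaten the trial's primary inference.

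**What to change.** In SAP 8.4.1:

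- Add multiple imputation of missing Week 6 OHSA#1 and PGI-S scores, with failure re-derived from the imputed scores and the primary model refitted. The sponsor should state the imputation model.
- Add the rerun that excludes every subject with a missing primary endpoint, alongside the sponsor-termination rerun.
- Add the difference in least-squares failure proportions between TD-9855 and placebo with its 95% CI.

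If any of these is dropped on purpose, list it in SAP 11.2 with the reason. All the data are already collected. The cost is SAP text and modest programming, with no change to sample size or the primary test.
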